4.2 Exclusion Criteria

Women who meet any of the following criteria will be excluded from this study:

- 4.2.1 Evidence of confirmed or probable active TB disease per WHO symptom screen and confirmation by Gene Xpert, shielded chest x-ray, or sputum sample
- 4.2.2 Participant report of personal history of INH- or rifampin-resistant, multi-drug resistant (MDR), or extensively drug-resistant (XDR) TB
- 4.2.3 Participant report of personal history of active TB in the past 2 years

- 4.2.4 Participant report of previous treatment for LTBI
- 4.2.5 Household contact (as defined above) with known active MDR or XDR TB disease
- 4.2.6 Known major fetal abnormality as detected on ultrasound
- 4.2.7 Known allergy/sensitivity or any hypersensitivity to components of study drugs or their formulation
- 4.2.8 Known history of liver cirrhosis at any time prior to study entry
- 4.2.9 Per participant report and/or medical records, evidence of acute clinical hepatitis, such as a combination of abdominal pain, jaundice, dark urine, and/or light stools within 90 days prior to entry
- 4.2.10 Participant report and/or medical records of peripheral neuropathy Grade 2 or higher within 90 days prior to entry
- 4.2.11 Current use or history of active drug or alcohol use or dependence that, in the opinion of the site investigator, would interfere with adherence to study requirements
- 4.2.12 Participant report and/or clinical evidence of porphyria
- 4.2.13 Any other condition that, in the opinion of the IoR/designee, would preclude informed consent, make study participation unsafe, complicate interpretation of study outcome data, or otherwise interfere with achieving the study objectives, including taking the study medication
- 4.2.14 Planned or current participation in an interventional drug study
- 4.2.15 Current use of any prohibited or precautionary medications (see Section 5.5), including didanosine (DDI) or stavudine (D4T)

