5.1 Regimens, Administration and Duration of Regimen

5.1.1 Regimens and Administration

The study drug regimen consists of 12 directly observed once-weekly doses of rifapentine (RPT) 900mg (six 150mg tablets), isoniazid (INH) 900mg (three 300mg tablets), and pyridoxine (vitamin B₆) 25mg to 100mg. HIV-1-infected and HIV-1-uninfected pregnant women with latent TB and their infants will be enrolled into two cohorts based upon gestation:

Cohort 1: Pregnant women in the second trimester (≥ 14 to < 28 weeks gestation).

Cohort 2: Pregnant women in the third trimester (≥ 28 to ≤ 34 weeks gestation) and postpartum.

Both cohorts will receive the study drug regimen weekly with food as described in the MOP. The study drug regimen dosing may be adjusted based on an interim analysis (see Section 10 (Clinical Pharmacology Plan)). Doses should be given 7 days part (± 2 days). Women will be provided a meal within 30 minutes prior to each dose. Following this meal, women will swallow whole RPT, whole INH, and whole or crushed pyridoxine tablets under direct observation of site staff (i.e., directly observed therapy, DOT).

Women must receive the appropriate dose of pyridoxine 25mg to 100mg based on the current local, national, or international dosing guidelines. Pyridoxine can be taken as a whole tablet or crushed.

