The Intensive PK sampling must be initiated on the same day (ideally in the morning) as the first dose of the study drug regimen, and conducted over the course of 72 hours according to the following time points: just prior to the first dose (t0), then 0.5h, 1h, 2h, 4h, 5h, 8h, 12h, 24h, 48h and 72h after the observed dose. Depending on site capacity, women may stay at the clinical research facility overnight after day 1 of the Entry Visit or return to the clinic at a designated time in the morning for administration of study drug and initiation of PK sampling. The same procedure can be followed for obtaining the PK samples at 48 and 72 hours after dosing.

Women will be asked to refrain from eating for two hours prior to each PK sampling dose of study drug, except for the meal provided by the site, which is to be eaten within 30 minutes before study drug administration. Women will be asked to refrain from further intake (except water) until three to four hours after the dose. The food type and quantity prior to each PK sampling dose will be recorded on CRFs.

RPT PK testing will be performed on all Intensive PK samples, after which, the t0 and 2h (or 4h) samples will be stored for later INH PK testing (see LPC for further details).

Women will be counseled about the signs and symptoms of active TB and asked to come to the clinic for an interim visit should any of the symptoms develop during the course of the study.

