6.3 Mother Weekly Visit (On Study Drug Regimen), Sparse PK Visit

Women will have weekly study visits while on the study drug regimen. Requirements for sequencing of procedures at the weekly visits are as follows:

- Before administering study drug regimen:
 - Prescribe study drug regimen per site SOP
 - Provide meal

The PK sampling visits are ideally conducted in the morning. The Sparse PK sample collection will be conducted on the visit of the woman's last dose of the study drug regimen over the course of 48 hours according to the following time points: 1h, 4h, 24h, and 48h after the observed dose. Women who are still taking study drug and breastfeeding postpartum will express breast milk, and plasma samples will also be drawn at the following time points:

- First weekly visit after delivery, three hours after the study drug dose
- Second weekly visit after delivery, six hours after the study drug dose
- Last dose visit, 24 hours after the study drug dose (breast milk collection only)

Women will be asked to refrain from eating for two hours prior to each PK sampling dose, except for the meal provided by the site, which is to be eaten within 30 minutes before study drug administration. Women will be asked to refrain from further intake (except water) until three to four hours after the dose. The food type and quantity prior to each PK sampling dose will be recorded on CRFs.

RPT PK testing will be performed on all Sparse PK samples, after which, the 1h and 4h samples will be stored for later INH PK testing (see LPC for further details).

Mother Weekly Visit Procedures (7 ± 2 days apart)		
Administrative and Regulatory		
 • Provide meal within 30 minutes prior to administering study drug
Behavioral and Counseling		
 • Signs and symptoms of active TB Counseling • Assess infant feeding methods (postpartum only)
Clinical		
 • Perform targeted physical exam • Record/update medical and medications history • Record/update AEs • Provide available test results • Assess TB symptoms, risk and exposure • Assess fetal movement and heart sounds (until delivery)

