9.2.2.3 Tolerability

- Permanent discontinuation of study drug regimen (i.e., RPT, INH, and pyridoxine)
- All AEs leading to permanent discontinuation of study drug regimen (i.e., RPT, INH, and pyridoxine)

9.2.2.4 RPT and des-RPT concentrations in breast milk of postpartum women receiving once-weekly RPT + INH.

9.2.2.5 Incidence of active TB in mother-infant pairs up to 24 weeks postpartum.

9.2.2.6 Estimates of CL/F, absorption, and volume of distribution of INH.

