Summary statistics will be compiled for plasma and cord blood RPT and des-RPT concentrations in infants collected within 72 hours following birth.

Dataset manipulation and data visualization will be performed using R v3.5.1 and Microsoft Office Excel.

Summary statistics

P2001 PHARMACOKINETIC ANALYSIS PLAN

Cord blood and plasma concentration data for RPT and des-RPT will be summarized by

- Count
- Minimum concentration and maximum concentration
- Mean and median
- First quantile and third quantile.

INH

Adults: Approach

Population-based estimates of PK parameters for INH (CL/F, absorption, volume of distribution) will be derived for all pregnant women irrespective of pregnancy trimester or pre-/post-partum status.

The study data, which provide a mix of longitudinal and cross-sectional observations, will be combined and modeled using nonlinear mixed effects approaches that are widely used in pharmacology research. Nonlinear mixed effects modeling will be performed using NONMEM v7.4. Dataset manipulation and data visualization will be performed using R v3.5.1 and Microsoft Office Excel. Perl-speaks-NONMEM (PsN) v4.8.1 and Xpose4 v4.6.1 will be used for model evaluation.

Exploratory data analysis

Prior to beginning modeling analyses, the following exploratory data analyses will be performed:

- Scatterplots of dependent variable (DV) versus time, stratified by treatment outcome, cohort, or disease status
- Summary statistics including the number of patients, samples, samples per patient, and number of patients with samples at each visit.

Structural model development

The absorption and disposition kinetics of INH will be described by a one compartment model with first-order (linear) elimination and first-order oral absorption. More complex models with respect to absorption, distribution, and elimination (e.g. mixture models) will be evaluated if necessary.

Goodness-of-fit diagnostic plots will be used to assess the structural model:

- Observations versus population and individual predictions
- Population, individual, and conditional weighted residuals versus time

Stochastic model development

Exponential error models will be used to characterize the between-subject-variability of the model parameters. A diagonal sigma-structure will be used, and off-diagonal elements may be included.

For continuous data, additive, proportional, and combined (additive and proportional) error models will be used to characterize the residual variability.

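### One of the four INH samples stored per woman is drawn before the first dose and none is later than 4 h, which weakens INH absorption estimates; redesignating one tube already drawn would help

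*Protocol*

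**What the plan says.** Protocol 6.2 draws eleven intensive PK samples at entry: "just prior to the first dose (t0), then 0.5h, 1h, 2h, 4h, 5h, 8h, 12h, 24h, 48h and 72h after the observed dose". Rifapentine (RPT) is assayed on all of them. For INH, "the t0 and 2h (or 4h) samples will be stored for later INH PK testing". Protocol 6.3 takes four sparse samples at the last dose (1, 4, 24 and 48 h), of which "the 1h and 4h samples will be stored for later INH PK testing". It also collects plasma at 3 h and 6 h from breastfeeding women still on drug, but does not designate those samples for INH. Both sections refer to the Laboratory Processing Chart (LPC) for details; it is not among the documents.

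Objective 2.2.8 is to explore INH population PK, and the outcome in 9.2.2.6 is "Estimates of CL/F, absorption, and volume of distribution of INH". The SAP's INH section pools the women: "Population-based estimates of PK parameters for INH (CL/F, absorption, volume of distribution) will be derived for all pregnant women irrespective of pregnancy trimester", and likewise irrespective of pre- or postpartum status. Its starting model is: "The absorption and disposition kinetics of INH will be described by a one compartment model with first-order (linear) elimination and first-order oral absorption". Richer structures may be tried where needed. The SAP names no INH precision target and no fixed or prior INH parameter.

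**The concern.** The t0 tube is taken before any study INH is given, and 4.2.4 excludes women by "Participant report of previous treatment for LTBI". Its expected INH concentration is therefore zero. That spends one of two entry assays, and one of four overall, on a sample that cannot inform CL/F, absorption or volume. What remains is 2 h (or 4 h) from entry plus 1 h and 4 h from the last dose. With the 2 h tube there are three distinct times for three structural parameters, all within 4 h of dosing. With the 4 h tube there are two. The choice of stored tube thus largely sets how well the INH outcome in 9.2.2.6 can be estimated, and more useful tubes are already being drawn.

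**Working it through.** **Plan's own figure.** There is none: Protocol 9.5 gives sample-size and precision figures for RPT only.

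**Inputs from the documents.** INH dose 900 mg (5.1.1); 50 evaluable women (9.4); sampling times (6.2, 6.3); the SAP's one-compartment model with first-order absorption and elimination.

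**Inputs assumed.** The documents give no INH parameters, so two sets are used.
- Set A: half-life 1.2 to 3.5 h, V 40 L, ka 1.5/h; between-subject variability 50/30/60% for CL/V/ka; proportional residual error 20%.
- Set B: 18 combinations of CL/F 10-35 L/h, V/F 50-80 L and ka 1-4/h; variability 50/20/60%; residual error 20%.

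**Step 1: information in t0.** With k = CL/V,

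C(t) = [Dose × ka / (V(ka − k))] × (e^(−kt) − e^(−ka·t)).

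At t = 0 the bracketed difference is 1 − 1 = 0 for every CL, V and ka. The derivatives are also zero, so t0 adds nothing. This needs no assumed parameter. For 50 women it concerns 50 × 1 = 50 of 50 × 4 = 200 INH assays.

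**Step 2: the 4 h tube for all women.** Only 1 h and 4 h are then informative. Three parameter sets show the ambiguity:

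| CL (L/h) / V (L) / ka (per h) | C(1 h), mg/L | C(4 h), mg/L | C(8 h), mg/L |
|---|---|---|---|
| 20 / 60 / 2 | 10.46 | 4.74 | 1.25 |
| 21.7 / 40.2 / 1 | 10.46 | 4.72 | 0.63 |
| 18.4 / 69.0 / 5 | 10.46 | 4.74 | 1.63 |

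The observed times cannot separate them, yet the 8 h values differ 1.63/0.63 = 2.6-fold.

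**Step 3: precision.** Population information for the fixed effects is M = Σ J′W⁻¹J, summed over women. J is the derivative of C with respect to log CL, log V and log ka; W = JΩJ′ + diag((0.2C)²); RSE = √diag(M⁻¹). This is a first-order approximation that treats variances as known and assumes both visits are complete, so it is optimistic. As a rough check, the same method applied to RPT, with the 40% variability of CL/F from Appendix II and an assumed 20% residual error, gives RSE(CL) 5.7%; Protocol Table 3 shows 5% at N = 50.

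| INH times (entry + last dose) | Set A: CL / V / ka RSE (%) | Set B: CL / V / ka RSE (%) |
|---|---|---|
| 2 h + 1, 4 h | 7.5-13.6 / about 11 / 21-23 | 7.4-37.5 / 4.3-37.7 / 18-67 (medians 9 / 7 / 32) |
| 4 h + 1, 4 h, all women | rank 2 of 3 | rank 2 of 3 in all 18 |
| Half the women 2 h, half 4 h | 7.5-16.6 / about 15 / 28-31 | ka 24-90 |
| 2, 8 h + 1, 4 h | about 7 / 5-6 / 11-13.5 | 7.2-8.5 / 3.6-6.6 / 11.6-50 (ka median 14) |
| 0.5, 8 h + 1, 4 h | not tabulated | 7.2-8.4 / 3.6-6.8 / 10.4-16.7 |

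Under Set B, if all women have the 4 h tube but actual times scatter with SD 5 min, the model regains full rank, with ka RSE 110-313%; with SD 15 min it is 38-89%.

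**Step 4: sensitivity of the gain.** At a 1.2 h half-life in Set A the predicted 8 h concentration is only 0.36 mg/L. Adding 0.5² to the residual variance (an assumed additive error of 0.5 mg/L) takes the RSE of V from 11.1% to 7.8% and of ka from 22.1% to 16.2%. The reductions are 1 − 7.8/11.1 = 30% and 1 − 16.2/22.1 = 27%, against roughly 50% with proportional error alone. In Set B's fast-absorption case CL/V/ka = 35/80/4, moving from 2 h to 2 h + 8 h takes ka only from 49.7% to 37.3%, a 25% reduction; 0.5 h + 8 h gives 15.0%.

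**The case against.** A reader might infer that INH CL/F, V and ka are all poorly estimated, or that the model fails wherever a site uses the 4 h tube. The documents support neither.

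- Protocol 6.2 names 2 h first and 4 h in parentheses, which reads as an alternate. The SAP pools all women, so some women on 4 h do not make the trial's model singular: with 20% on 4 h, Set A gives V about 12% and ka 23-25%. Singularity needs every woman on 4 h, nominal times and no constrained parameter.
- With the 2 h tube, CL and V are fair under most assumptions. At a 1.2 h half-life, adding 8 h moves CL only from 7.5% to 7.2%; at 3.5 h it moves from 13.6% to 7.3%.
- No INH precision standard is missed. The 5% RSE benchmark in 9.5.1 sits under RPT clearance, and objective 2.2.8 is secondary and exploratory.
- A t0 assay is not worthless. Absence of prior LTBI treatment rests on participant report, and Protocol 1.1 notes that WHO recommends daily INH for HIV-infected pregnant women. A t0 result could reveal undisclosed use. The documents do not give this as its purpose.
- The LPC may specify other tubes or a rule for 2 h versus 4 h.

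All of this stands as a limit on scope and size. None of it gives t0 any information on the parameters in 9.2.2.6, or explains why no tube after 4 h is kept for INH.

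**Conclusion.** The point holds as a modest design weakness. Two parts rest on no assumed INH value: t0 is uninformative for CL/F, ka and V under the SAP's model, and two distinct post-dose times cannot determine three structural parameters.

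The size of the loss does depend on assumptions. With the 2 h tube it falls mainly on ka (RSE about 21-23% in Set A, 18-67% in Set B), and on CL and V when elimination or absorption is slow. A 2 h/4 h mix stays estimable with poorer ka. Non-identifiability is a conditional risk that 6.2 leaves open, not the expected result.

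The three-time fit also takes 2 h only from entry and 1 h only from the last dose, so it leans on INH PK being the same at both visits, which the SAP's pooled model does not test. The RPT analyses and the primary conclusions are unaffected.

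**What to change.** In Protocol 6.2, and in the LPC if it says the same, store for INH the 2 h tube plus one later tube already drawn, for example 8 h, in place of t0. Remove the 4 h alternative, or limit it to women whose 2 h tube is missing. Before choosing the later tube, check it against the INH assay's quantification limit; if fast absorption is thought likely, compare 0.5 h + 8 h, which holds ka better across Set B.

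Under Set A this cuts the RSE of V and ka by about 30-50%, the lower end applying if assay error at low concentrations is material. The ka gain from 2 h + 8 h can be smaller if absorption is fast.

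The cost is wording in 6.2 and the LPC: the same number of INH assays, no extra blood, and no change to the RPT assay on t0. INH testing follows RPT testing, so enough plasma must remain in the later tube. What is lost is a pre-dose check for undisclosed INH use. If the team wants that check, 6.2 should say so and an additional late tube should be assayed, at the price of one more assay per woman.

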6.3 Mother Weekly Visit (On Study Drug Regimen), Sparse PK Visit

Women will have weekly study visits while on the study drug regimen. Requirements for sequencing of procedures at the weekly visits are as follows:

- Before administering study drug regimen:
 - Prescribe study drug regimen per site SOP
 - Provide meal

The PK sampling visits are ideally conducted in the morning. The Sparse PK sample collection will be conducted on the visit of the woman's last dose of the study drug regimen over the course of 48 hours according to the following time points: 1h, 4h, 24h, and 48h after the observed dose. Women who are still taking study drug and breastfeeding postpartum will express breast milk, and plasma samples will also be drawn at the following time points:

- First weekly visit after delivery, three hours after the study drug dose
- Second weekly visit after delivery, six hours after the study drug dose
- Last dose visit, 24 hours after the study drug dose (breast milk collection only)

Women will be asked to refrain from eating for two hours prior to each PK sampling dose, except for the meal provided by the site, which is to be eaten within 30 minutes before study drug administration. Women will be asked to refrain from further intake (except water) until three to four hours after the dose. The food type and quantity prior to each PK sampling dose will be recorded on CRFs.

RPT PK testing will be performed on all Sparse PK samples, after which, the 1h and 4h samples will be stored for later INH PK testing (see LPC for further details).

Mother Weekly Visit Procedures (7 ± 2 days apart)		
Administrative and Regulatory		
 • Provide meal within 30 minutes prior to administering study drug
Behavioral and Counseling		
 • Signs and symptoms of active TB Counseling • Assess infant feeding methods (postpartum only)
Clinical		
 • Perform targeted physical exam • Record/update medical and medications history • Record/update AEs • Provide available test results • Assess TB symptoms, risk and exposure • Assess fetal movement and heart sounds (until delivery)
Laboratory	Blood	Collect blood for: 
 • Sparse PK sample collection (during the visit of the last dose and 48 hours following) • Plasma sample collection (breast milk PK participants only, conducted first and second week postpartum) • Complete blood count (every four weeks) • Liver Function Test (every four weeks) • Coagulation profiles (at one visit at ≥34 weeks gestational age only)
	Breast milk	Collect breast milk for: 
 • Breast milk PK sample collection (if eligible, conducted first and second week postpartum and on the visit of the last dose)
Study Product		
 • Prescribe (according to local guidelines) and administer RPT, INH, and pyridoxine under DOT

6.4 Mother Monthly Visits (Post-study drug regimen) and Study Exit Visit

The change from the weekly visit schedule (on study drug regimen) to the monthly visit schedule (post-study drug regimen) is independent of the woman's delivery date. It is possible that a woman enrolled in Cohort 1 could continue the study drug regimen postpartum (e.g., if she delivers her infant pre-term). Following the completed study drug regimen, all women will be followed once monthly (i.e., every four weeks counting from labor and delivery, ideally coinciding with infant monthly visits) until 24 weeks postpartum to assess for the development of active TB disease. At the final weekly visit, follow-up dates for the monthly visits will be provided to the woman. Contact information will also be obtained to improve retention if a visit is missed. A woman who does not present for a follow-up visit within two weeks of the scheduled visit will be considered as having missed that study visit.

There is no required sequencing of procedures at these visits.

The final study visit for women will occur 24 weeks postpartum and will ideally be scheduled to occur on the same day as the Infant Study Exit Visit.

Mother Monthly Visit and Study Exit Visit Procedures (± 2 weeks)	
Administrative and Regulatory	
 • None
Behavioral and Counseling	
 • Signs and symptoms of active TB Counseling • Assess infant feeding methods (postpartum only)
Clinical	
 • Complete physical exam • Record/update medical and medications history • Record/update AEs • Provide available test results • Assess TB symptoms, risk and exposure • Assess fetal movement and heart sounds (until delivery)
Laboratory	
Collect blood for (no blood is collected at the Study Exit Visit):
 
 • Complete blood count • Liver Function Test • Coagulation profiles if clinically indicated (e.g., bleeding event)

6.5 Infant/Newborn Visit

The infant single PK sample collection will be conducted within three days of life, ideally in the morning. When a study participant is admitted for delivery, the research team should be notified (i.e., the medical records may indicate that the patient is enrolled in IMPAACT 2001, and the research staff's contact information may be available). The participants may also be asked to contact the research staff once they are in labor. The infant single PK sample will only be collected if the mother's most recent dose was taken within 72 hours of drawing the infant's blood.

At sites with capacity, cord blood PK sample collection will be offered to mothers to be conducted during labor and delivery. See Section 10 below for details and eligibility of the single PK sample and cord blood sample collections. Eligibility for single PK sampling must be confirmed prior to collection of this sample.

Infant/Newborn Visit Procedures (within 3 days of life)	
Administrative and Regulatory	
 • None
Clinical	
 • Assess eligibility for single PK sampling • Complete physical exam • Record medical and medications history • Record AEs • Provide available test results to mother
Laboratory	Collect blood for: 
 • Single PK sample collection (if eligible) • Coagulation profile (if eligible) • Cord blood (optional if eligible, during mother's delivery)

